Most data describing HRQoL after kidney transplantation have been collected from adult populations (median age ~ 50 years) (4, 8). Information on if/how HRQoL of older ESRD patients change during different phases of the treatment (dialysis, early post transplantation and long term transplantation) is very sparse (4) and for older patients the documentation is restricted to small cross sectional studies comparing a group of older recipients with either older patients on dialysis treatment or younger transplant recipients (9, 10). To our knowledge, no prospective study describing HRQoL longitudinally in older patients from pre-transplant through the immediate, short term and long-term phases post-transplant has been published. In 2018, RN [name] defended her PhD thesis on basis on the QUESTION65 study describing the short term HRQoL effects of kidney transplantation in the elderly (11-13). Consequently, there is a knowledge gap concerning how kidney transplantation affects HRQoL in the long term compared to the alternative; lifelong dialysis treatment.

Date of Update: April 5. 2020

Older patients with ESRD often have a high burden of co morbidities. The most widely used comorbidity index is the Charlson comorbidity index (CCI) (14). The CCI has been validated in several populations including patients with ESRD (15). In recipients older than 70 years, the CCI has, however, not been shown to be associated with survival after kidney transplantation (16). More recently, other comorbidity scores have been developed for patients with ESRD (17, 18). However, these indexes are not validated in the elderly. We are consequently lacking instruments validated in older transplant candidates for standardized measurement of comorbidity.

Even though kidney transplantation is regarded as the most cost-effective treatment of ESRD, to our knowledge no proper health economic evaluation of transplantation in older patients exists.

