We hypothesize that selection criteria of elderly recipients with ESRD can be improved by combining data from a pre-transplant comorbidity score and self-reported health related quality of life (HRQoL). We believe our research will improve the individual evaluation of each patient and provide each patient with the best treatment option available, both with respect to survival and quality of life. By identifying patients who will *not* benefit from transplantation, the organ can be allocated to another patient on the waiting list, thereby reducing the waiting time. The findings will be of strategic importance for future treatment of all patients in Norway with ESRD, regardless of age.

Added value for the society: Improved selection criteria combined with health economic evaluation will provide important guidance in the search for cost-effective treatment algorithms which is necessary if we should be able to utilize our health budget optimally. Evidence of the cost-effectiveness of various treatment options is required to facilitate appropriate resource planning and develop optimal treatment models across diverse health care settings. Policymakers need evidence that an intervention or program of care represents the most efficient use of available resources and

Date of Update: April 5, 2020

provides value for money. Health economic evaluation is a systematic way of producing this evidence (19).

3. Aims

The overall aim of this study is to collect and evaluate long-term data on patient reported, clinical and health economic outcomes following kidney transplantation in older patients (≥ 65 years of age at enlisting). Further specific aims are:

Aim 1:

To evaluate patient reported HRQoL longitudinally from time of wait listing and up to 5 years after transplantation in kidney transplant candidates older than 65 years of age.

These data will describe if and how patient reported HRQoL changes over time and thereby evaluate whether the benefit of transplantation described for general adult patients is also valid for older recipients. The data will also make it possible to compare the effect on HRQoL and clinical outcomes for patients on long-term dialysis compared to patients several years after transplantation.

Aim 2:

To investigate the relationship between pre-transplant comorbidity, expressed as the Liu comorbidity index and post-transplant HRQoL at 1-3 years post transplant.

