4.1. Design, methods and analyses

Statistics

All statistical analyses will be performed using the statistical software package SPSS Statistics version 22 or later. Scores from KDQOL-SF will be calculated and compared using traditional statistical methods (two-sided unpaired t-test or paired t-test, ANOVA, logistic regression). Fisher's exact test will be used to analyze binary data. Other standard statistical methods as for example multiple variable logistic regression analyses will be used as needed. Survival analyses will be performed using the Kaplan-Meier method and Cox proportional hazard models.

Aim 1:

Data collection: Patient reported outcomes are collected in an on-going, prospective, longitudinal study (QUESTION65). By the end of inclusions in December 2016, we estimate that 280 patients should be included. All patients give their written informed consent before inclusion in the study. In addition, all patients have signed an informed consent when they were included in the Norwegian Renal Registry. This allows the use of unidentified data from the registry in research protocols.

HRQoL is assessed using the KDQOL-SF-36 health Survey (20, 21). This survey consists of two parts, a generic (SF-36) and disease specific (KDQOL) part. The same questionnaire is used before and after transplantation. The results will also be compared with data from an age matched Norwegian cohort (22).

All patients over the age of 65 years, who are accepted for the kidney transplantation waiting list or living donor transplantation, receive an invitation to participate in the study. In addition to provide baseline data, all patients receive additional forms with the same questionnaires every sixth months until they are transplanted, permanently removed from the transplant waiting list or deceased. Patients who are transplanted will receive a discharge form from Rikshospitalet (10 weeks after transplantation), after six months and at one-, three-, five-, seven- and ten years post-transplant.

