Statistical power: The primary objective of the study is to detect differences in the QOL dimension general health (GH). According to the literature, SF-36 scores for GH varies between 47 and 69 for transplanted patients and between 36 and 44 for patients treated in haemodialysis (10, 23, 24). The standard deviation in these studies varies between 15 and 25. A clinically significant difference in SF-36 GH score is estimated to be around 10%. With a predicted SF-36 GH score of 50 for transplanted patients and 40 for patients in haemodialysis, we need a minimum of 63 patients to complete the study to reach a significance level (α) of 5% and a power (β) of 80%. According to previous analyses, 80% of patients > 70 years who are accepted for the kidney transplantation wait list will eventually be transplanted and five year survival in this age group is 64% (5). Consequently, a minimum of 100 patients must be transplanted and hence, an even higher number must be included at baseline. To have the possibility to evaluate the impact of gender and dialysis modality, the number of included patients has been further increased up to a total of 280. The regional committee of medical and health research ethics have approved this increase.

By August 2016, 261 patients are included, 152 are transplanted. Consequently, the number included and transplanted patients are already well above the minimum number.

Aim 2:

Data collection: From 2012 we have included pre-transplant data according to the Liu comorbidity index (17) as part of the routine work up of candidates for kidney transplantation. Complete data describing patient and transplant characteristics, including the Liu comorbidity index will be

Date of Update: April 5. 2020

extracted from the Norwegian Renal Registry. The data will be exported from the registry without any identification except from a patient number. Post-transplant HRQoL values will be retrieved from the QUESTION65 database.

Statistical power: No previous studies describing the correlation between pre-transplant comorbidity and post-transplant HRQoL exist. Based on the same considerations as described for Aim 1, a similar number of patients should be necessary for Aim 2 to reach a significance level of 5% and a power of 80%.

Aim 3:

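### HRQoL forms stop at permanent removal from the waiting list, so Aim 1 cannot support the stated comparison of HRQoL on long-term dialysis with HRQoL several years after transplantation

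*Combined protocol and SAP*

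**What the plan says.** The background names as a knowledge gap "how kidney transplantation affects HRQoL in the long term compared to the alternative; lifelong dialysis treatment". Under Aim 1, Section 3 adds that the data will make it possible to "compare the effect on HRQoL and clinical outcomes for patients on long-term dialysis compared to patients several years after transplantation".

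Section 4.1 (Aim 1, Data collection) sets the form schedule. After baseline, untransplanted patients receive forms "every sixth months until they are transplanted, permanently removed from the transplant waiting list or deceased". Recipients receive them at 10 weeks and six months, and then "at one-, three-, five-, seven- and ten years post-transplant". The only outside HRQoL comparator is named in the sentence "The results will also be compared with data from an age matched Norwegian cohort"; its reference is titled as normative data from the general Norwegian population.

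The Aim 1 power statement is itself framed as transplant against dialysis: "With a predicted SF-36 GH score of 50 for transplanted patients and 40 for patients in haemodialysis".

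**The concern.** A patient who is never transplanted must eventually be removed from the list or die, and either event ends the forms. A patient who is removed and stays on dialysis therefore leaves HRQoL follow-up just when transplantation is no longer an option. Recipients, by contrast, have a long-term schedule.

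The two sides of the comparison are thus observed under different rules. Late forms from untransplanted patients come only from those who are alive and still accepted for transplantation. The statement at stake is the one that addresses the background's knowledge gap. The SF-6D values for the dialysis side of the Aim 4 cost-effectiveness ratio come from the same QUESTION65 forms and carry the same limit.

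**Working it through.** **1. Is HRQoL after removal supplied elsewhere?** Not in the text available for this review, which lacks the part between the Aim 4 power statement in Section 4.1 and Section 4.3. Under Aims 2 and 3 the Norwegian Renal Registry supplies patient and transplant characteristics, comorbidity and survival, while HRQoL comes from QUESTION65. Section 4 would retrieve missing data from patient records, but a questionnaire that was never sent will not be there.

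**2. The plan's own sample size.** Inputs from Section 4.1: GH scores of 50 and 40, two-sided 5% level, 80% power. On the SD the plan says only "The standard deviation in these studies varies between 15 and 25".

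n per group = 2 × SD² × (1.96 + 0.84)² / 10²

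- SD 15: 36
- SD 20: 63
- SD 25: 99

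The stated 63 is reproduced as a per-group number at SD 20. The corresponding total would be 126, so a dialysis group of 63 is implied as well. Only the transplanted group is inflated for survival: 63 / 0.64 = 98.4, against the stated 100. No number is planned for a long-term dialysis group.

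**3. How many could still be receiving forms late?** Inputs: 289 included and 214 transplanted (background), leaving 75 who are waiting, removed or dead in unknown proportions; mean wait 9-12 months over the last decade, since then markedly longer with no figure given (Section 2.1). I assume exponential waits and ignore deaths and removals, so within this model the counts are upper bounds. The 18- and 24-month rows are assumptions.

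Still waiting at t months = 289 × exp(−t / mean wait)

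| Mean wait (months) | 3 years | 5 years |
|---|---|---|
| 9 | 5.3 | 0.4 |
| 12 | 14.4 | 1.9 |
| 18 | 39.1 | 10.3 |
| 24 | 64.5 | 23.7 |

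**4. What such numbers could detect.** The plan's 64% five-year survival gives 214 × 0.64 = 137 surviving recipients. With SD 20 and a 10-point difference:

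power = Φ(10 / [20 × √(1/n + 1/137)] − 1.96)

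- n = 2: 10%
- n = 5: 19%
- n = 14: 43%
- n = 24: 62%
- n = 39: 79%
- n = 64: 91%

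About 41 patients give 80% power (21 at SD 15, 77 at SD 25). The figure of 137 is a five-year count. The documents give no three-year survival, so I use it there too; at small n the untransplanted group dominates the result.

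**5. What continued follow-up could have added.** If 80% are eventually transplanted, 0.20 × 289 = 58 never are. The documents give no survival on dialysis. Assuming 30-50% alive at five years leaves about 17-29 patients, with power of about 49-69% against 137 recipients.

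**The case against.** The strongest reply is that the shortage of late data depends on the assumed wait. Section 2.1 says that waits have become longer, and Section 4.1 reports 261 included and 152 transplanted by August 2016, leaving 109 (42%) untransplanted. With even accrual over 48 months (assumed), the expected number still waiting is 261 × (m/48) × (1 − exp(−48/m)): about 49 for m = 9, 64 for m = 12 and 113 for m = 24. The 109 also includes deaths and removals, so this is a warning rather than proof. Even so, a reader who infers that there will be almost no late data goes too far at three years: a 24-month mean would leave more than the 41 needed, before deaths and removals. The exponential model also implies that everyone is eventually transplanted, which conflicts with the plan's 80%.

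Two further inferences are tempting but unsupported:

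- **That the missing patients make dialysis HRQoL look too good, so that the transplant advantage is understated.** The documents give no reasons for removal, and recipients at five years are themselves a surviving 64%. The net direction is unknown.
- **That the 58 never transplanted are the long-term dialysis patients.** The 80% is quoted for patients over 70, some of the 58 will have died while listed, and living-donor candidates may not be on dialysis at all.

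It is also fair to say that time since listing is not time on dialysis, that the plan does not define long-term dialysis, and that the sentence at issue is an addition to Aim 1's main objective. These points limit the size of the problem. They do not supply HRQoL from patients who remain on dialysis after removal.

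**Conclusion.** The collection rule does not support the Aim 1 statement about HRQoL on long-term dialysis. The absence of forms after removal follows directly from Section 4.1 and needs no assumption. The number of late forms does need one: about 5-14 at three years and 0-2 at five for a 9-12 month mean wait, rising to about 64 and 24 for 24 months. Five-year data therefore fall short of the 41 needed at SD 20 throughout this range, whereas three-year data may or may not. Whatever its size, the late group is selected by survival and continued eligibility.

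The finding does not extend to Aim 1 as a whole. Within-patient change from listing to five years after transplantation stands, as does the clinical-outcomes half of the sentence in Section 3. Waiting-list HRQoL is still collected and can be compared with post-transplant HRQoL under that name.

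**What to change.** - Restrict the Aim 1 HRQoL comparison to patients while active on the waiting list, and delete the claim about HRQoL on long-term dialysis.
- Apply the same restriction when interpreting dialysis-side SF-6D values in Aim 4.
- Report the number of patients permanently removed, the reasons, and the number of forms received by time since listing.
- Where consent and ethics approval allow, stop treating removal as the end of HRQoL follow-up, and send the same form to living delisted patients at time points still reachable. Inclusion was to end in December 2016 and the protocol is dated April 2020, so one- and three-year forms after listing can no longer be collected; five years or later is what remains. Section 6 says that Aim 1 data collection was completed in November 2016, while Section 4.4 schedules it in 2019 and expects a complete database by the end of 2020. These statements should be reconciled first.

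The restriction costs wording and a narrower conclusion. The added follow-up costs a few dozen forms at most, plus whatever approval is needed, and the late comparison may still fall short of 80% power.

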Our research group has previously initiated a prospective study including kidney transplant candidates older than 65 years who are listed for transplantation at Oslo University Hospital, Rikshospitalet (QUESTION65). At present, 289 patients are included and 214 have been transplanted. Results have been presented at top international conferences (ERA-EDTA, ASN, ESOT, ATC). The first PhD protocol using data from this study was started in 2015 (PhD student [name]) the protocol focusing on short- and intermediate-term changes in HRQoL, effect of comorbidity on short-term complications and HRQoL and a qualitative evaluation of the patients' expectations.

For patients with end stage renal disease (ESRD), kidney transplantation is in general considered as the best treatment-option both with respect to survival (1), costs (2, 3) and HRQoL (4). Selected older patients have also been shown to improve survival after transplantation compared to dialysis (5, 6). For decades Oslo University Hospital, Rikshospitalet has been Europe's largest kidney transplantation center.

As a result of the general aging of the population, the number of older individuals with chronic diseases including chronic kidney disease is expected to increase significantly over the next 25 years. Consequently, the number of older kidney transplant candidates will also increase. Contrary to most other countries in the world, Norway has never had any upper age limit for kidney transplantation. In spite of this, we have had among the shortest waiting-time worldwide (7). Due to organ scarcity, transplant centers often have an upper formal or practical age limit for potential recipients. In some countries patients older than 50-55 years may end up spending the rest of their life in hemodialysis. The major challenge concerning allocation of donor organs is to find those patients who will derive the most benefit of transplantation in terms of improved patient outcome, less complications and increased survival time. Today, most centers use the same medical criteria for all patients, regardless of age. Based on the literature there is, however, a knowledge gap between what is documented for older patients versus younger patients.

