Detection of any association between pre-transplant comorbidity and post-transplant HRQoL, can improve the selection process of older transplant candidates by including the comorbidity score as part of the patient selection algorithm.

Aim 3:

To investigate the relationship between pre-transplant comorbidity, expressed as the Liu comorbidity index, pre-transplant HRQoL described by KDQOL-SF and post-transplant patient- and graft survival.

Aim 4:

To evaluate kidney transplantation in older patients in a health economic perspective, including evaluation of quality adjusted life years (QALY), and investigate if QALY values are changing over time. By collecting standard cost estimates for the different procedures, we should be able to calculate an incremental cost-effectiveness ratio (ICER) for kidney transplantation versus dialysis

This aim will provide further information about the benefits kidney transplantation can or cannot provide older patients from a health economic perspective. This analysis will be of major importance for present and future priority discussions.

4. Implementation

Data will be retrieved from the QUESTION65 database described previously, and the Norwegian Renal Registry. Missing data will be retrieved from the patient records at Oslo University Hospital, Rikshospitalet and from the patients' local hospital records. The key necessary for identification of patients will be stored at the registry and will not be available for the researchers.

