Data collection: Complete data describing patient and transplant characteristics, including the Liu comorbidity index will be extracted from the Norwegian Renal Registry as described for Aim 2. Pre-transplant HRQoL will be retrieved from the QUESTION65 database. Post-transplant survival data will be extracted from the Norwegian Renal Registry. The data will be exported from the registry without any identification except from a patient number.

Statistical power: No previous studies describing the correlation between pre-transplant comorbidity, pre-transplant HRQoL and post-transplant survival exist. Based on previous analyses on similar patient cohorts (25), 150 patients should be sufficient to detect statistically significant associations.

Aim 4:

Data collection: QALYs will be calculated from the SF-36 (SF-6D) scores available in the QUESTION65 database. From the SF-6D, a health index can be calculated. Patients who die during follow-up will have health index = 0 from time of death, and with this health index, QALYs can be calculated for each patient during follow-up. Costs necessary for estimation of cost/QALY and ICER will be estimated through use of information from the patient records at the patients' local hospitals as well as Oslo University Hospital. DRG weighted costs will be used for each contact (in-patient, out-patient and dialysis). In addition, medication costs will be estimated based on each patient's medication list and travel costs will be estimated based on the distance between the patient's home and the hospital.

Statistical power: No previous studies evaluating QALY in older kidney transplant recipients exist. Power calculation is therefore difficult to perform.

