4.3. Budget

Budget (in NOK 1000)	2019	2020*	2021	2022	Total
Personnel costs (PhD student)	955	0	955	955	2865
Travel grant	30	0	30	30	90
Other operating costs: Courses, Literature	15	0	15	15	45
Total	1000	0	1000	1000	3000

* No expences registered for 2020 because the PhD student is on maternity leave

4.4. Schedule:

Activity	2019	2020	2021	2022
Data collection of HRQoL study - aim 1	x			
Data collection - aim 2	x	x	x	
Data collection - aim 3	x	x	x	
Data collection - aim 4	x	x	x	x
Data analysis	x	x	x	x
Publication		x	x	x
Writing PhD thesis				x
Dissertation for the degree of PhD				x

Date of Update: April 5. 2020

Five years HRQoL data will be available for the first patient in 2018 and by the end of 2020, the database is expected to be complete also with long-term data necessary for evaluating long-term HRQoL (aim 1). Data from the other aims will be available for analysis and evaluation from 2019.

Planned publications: All manuscripts will be published in international nephrology, transplant or geriatric journals. Abstracts will be presented at international meetings.

Tentative papers:

1. Changes in health-related quality of life in older kidney transplant recipient up to three years post-transplant (2020)
2. Association between pre-transplant comorbidity and health related quality of life in older kidney transplant recipients (2021)
3. Association between pre-transplant comorbidity, pre-transplant health related quality of life and long-term (three years) post-transplant survival in kidney transplant recipients older than 65 years (2021)
4. Cost-effectiveness of kidney transplantation in the elderly (2022)

4.5 Implementation plan:

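### Does the missing follow-up limit and event count for Aim 3 put its survival analysis at risk?

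*Combined protocol and SAP*

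**What the plan says.** Section 3 defines Aim 3 as relating the Liu index and "pre-transplant HRQoL described by KDQOL-SF and post-transplant patient- and graft survival", with no time point. Section 4.1, under Statistics, names Kaplan-Meier and Cox models with no truncation or censoring rule. Section 4.1, Aim 3, takes survival from the Norwegian Renal Registry and, citing earlier analyses of similar cohorts, states that "150 patients should be sufficient to detect statistically significant associations".

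Three years appears for this aim only in section 4.4, in the list of tentative papers, where paper 3 (dated 2021) is to cover "long-term (three years) post-transplant survival in kidney transplant recipients older than 65 years". The schedule row "Data collection - aim 3" is marked for 2019 to 2021, and the text below it adds: "Data from the other aims will be available for analysis and evaluation from 2019".

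Aim 3 is not the main objective. Section 4.1, Aim 1, states: "The primary objective of the study is to detect differences in the QOL dimension general health (GH".

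**The concern.** Power in a Cox model depends on the number of events, so a count of patients cannot by itself show that the analysis is large enough. Aims 1 and 2 at least state 5% and 80%; Aim 3 states neither.

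Follow-up length is also the main way left to gain events, because inclusion ended in 2016. Many recipients will have been followed well beyond three years. If the paper title were applied as a limit, every later death and graft loss would be discarded and only fairly strong associations would be detectable. A null result from so few deaths could be misread as no association, on an aim that serves the protocol's hypothesis about better patient selection. A horizon left unstated could also be chosen after the survival data have been seen.

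**Working it through.** **The plan's own figure.** The 150 cannot be reproduced: the protocol gives no hazard ratio, event count, follow-up, significance level or power for it. It rests on a cited cohort that is not part of the documents. The background section reports that "289 patients are included and 214 have been transplanted", so the number available exceeds 150.

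**Inputs from the protocol.** 214 recipients; 152 of them transplanted by August 2016; five-year survival 64%, quoted for patients over 70; first transplant about 2013, inferred from "Five years HRQoL data will be available for the first patient in 2018".

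**Assumptions.** Even accrual from January 2013 to August 2016 (152) and then to mid-2018 (62); constant hazard; 80% five-year survival as an optimistic bound, since the study takes patients from 65.

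**Deaths within three years.** With survival S(t) = S5^(t/5), the three-year risk is 1 − S5^0.6.
- S5 = 0.64: 1 − 0.64^0.6 = 0.235; 214 × 0.235 = 50.3.
- S5 = 0.80: 1 − 0.80^0.6 = 0.125; 214 × 0.1253 = 26.8.

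At the end of 2020 the latest recipients have not reached three years, so the counts are 50.0 and 26.7.

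**Deaths without truncation, end of 2020.** For follow-up spread evenly between a and b years, mean risk = 1 − (e^(−λa) − e^(−λb)) / (λ(b − a)), with λ = −ln(S5)/5. The first 152 have 4.4 to 8.0 years, the other 62 have 2.5 to 4.4 years.
- S5 = 0.64 (λ = 0.0893): 64.1 + 16.3 = 80.4.
- S5 = 0.80 (λ = 0.0446): 36.6 + 8.8 = 45.4.

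The same formula at the end of 2021 gives 91.9 and 52.7.

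**Loss if three years were a limit (end of 2020).** 1 − 50.0/80.4 = 38%; 1 − 26.7/45.4 = 41%. The share depends little on the number of recipients, but it does depend on the hazard shape: for Weibull shapes 0.7 to 1.4 and S5 from 64% to 80%, the ratio of untruncated to truncated deaths runs from 1.4 to 2.2.

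**Detectable hazard ratio** per SD of one predictor, two-sided 5%, 80% power: exp(2.8016/√D), D being the number of deaths.

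| Follow-up | Deaths (S5 64% / 80%) | Detectable HR |
|---|---|---|
| Three-year limit | 50.0 / 26.7 | 1.49 / 1.72 |
| To end of 2020 | 80.4 / 45.4 | 1.37 / 1.52 |
| To end of 2021 | 91.9 / 52.7 | 1.34 / 1.47 |

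**Is longer follow-up always better?** Take HR 1.4 up to year three and a different HR afterwards. Power = Φ(b√D − 1.96), where b is the event-weighted mean of the early and late log hazard ratios. At the end of 2020 with S5 = 0.64:
- later HR 1.4, 1.3, 1.2, 1.1: power 85%, 79%, 70%, 59% untruncated;
- truncated at three years: 66% throughout.

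Break-even late log HR = ln(1.4) × (√(50.0 × 80.4) − 50.0)/(80.4 − 50.0) = 0.3365 × 0.441 = 0.148, an HR of 1.16. Below that, truncation has more power.

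**Is there a limit at all?** The aim, the methods and the data collection text contain none. Titles in the same list do not fix analysis windows reliably: paper 1 covers quality of life up to three years, while Aim 1 plans it up to five.

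**The case for a change.** The best case for a change is that the gap is real on any assumption and closing it costs only wording. A censoring date, the meaning of three years and the treatment of death in graft survival could be fixed before analysis, and expected events could replace the 150. Since 152 recipients had been transplanted by August 2016, about 126 would be more than five years past transplantation at the end of 2020 (152 × 3.0/3.62 under even accrual), so the events at stake are not trivial.

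What stands is that the text is thin and that some freedom of choice remains. That freedom is narrow: a registry extract has a date, Cox models use all follow-up to it unless told otherwise, and both the horizon and the graft-failure definition will show in the paper. The loss of events depends on a reading that no section supports. The end of 2021 also fits poorly with a paper planned for 2021. Expected events worked out now would describe the study without enlarging it.

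**Conclusion.** The concern does not call for a change. The omission is a gap in detail that analysts would fill sensibly: follow-up to the date of the registry extract, with three-year survival reported from the Kaplan-Meier curve. On that course no events are lost. Had three years been meant as a limit, about 40% of the deaths expected by the end of 2020 would go, assuming constant hazard and the accrual pattern above. That would be a fair trade-off rather than an error: follow-up would be nearly uniform, the result would lean less on proportional hazards, and power would be higher if the effect faded below a later HR of about 1.16 from an early 1.4.

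The death counts are illustrations. They use all 214 recipients without allowance for missing predictors or correlation between them, and an assumed 80% survival at the lower end. They cover deaths only, because the protocol gives no graft survival rate. The 150 cannot be checked from the documents, which is different from being too small.

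### Aim 4 scores deaths as 0 but scores the living only from returned SF-6D forms, with no rule for missing forms, so mean QALYs can be biased downward

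*Combined protocol and SAP*

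**What the plan says.** Under Aim 4 in Section 4.1, "QALYs will be calculated from the SF-36 (SF-6D) scores available in the QUESTION65 database". The same paragraph adds that "Patients who die during follow-up will have health index = 0 from time of death", and that on this basis "QALYs can be calculated for each patient during follow-up". The QALYs feed an ICER for transplantation against dialysis (Section 3, Aim 4).

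The form schedule is given under Aim 1 in Section 4.1. After baseline, waiting patients are due forms "every sixth months until they are transplanted, permanently removed from the transplant waiting list or deceased". Recipients are due forms at 10 weeks, 6 months, and 1, 3, 5, 7 and 10 years.

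The only general statement on missing data is in Section 4 (Implementation): "Missing data will be retrieved from the patient records at Oslo University Hospital, Rikshospitalet and from the patients' local hospital records". The Statistics paragraph of Section 4.1 names no missing-data method. Registry follow-up for death is stated under Aim 3, for recipients: "Post-transplant survival data will be extracted from the Norwegian Renal Registry".

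**The concern.** A death gets its value without a form, whereas a living patient gets one only if the form came back. Hospital records cannot be relied on to supply self-reported SF-36 answers that were never given. Aim 4 also leaves open how the time between forms is filled, what the horizon is, and what happens to a living patient after permanent delisting. From then on no form is due, but a later death could still be entered as 0.

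If the calculation keeps all deaths but uses only those living patients who responded, the dead are over-represented in the group mean. This happens even when non-response is unrelated to health. Scoring death as 0 is correct in itself, and a given patient's own QALY need not be wrong. The distortion lies in the mean. That mean enters an ICER which the plan intends for priority-setting discussions.

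**Working it through.** Aim 4 gives no QALY, return-rate or sample-size figure, so there is nothing of its own to reproduce. The check asks how far the mean moves when the truth is known and the groups are identical.

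**Inputs.** Five-year survival is S(5) = 0.64 (Section 4.1, Aim 1 power paragraph, patients over 70), applied to both groups as an assumption. The hazard is constant: λ = -ln(0.64)/5 = 0.0893 per year. The index in the living is 0.70 (assumption). The return probability r per form is the same for every form and independent of health (assumption; the documents give none). Form times are as in Section 4.1.

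**True mean QALY.** 0.70 × (1 - S(H))/λ.
- Five years: 0.70 × 0.36/0.0893 = 2.82.
- Three years: S(3) = 0.765, which gives 1.84.
- The true difference between groups is 0.

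**Rule A: visit-wise available values.** At each visit the mean is 0.70 × rS/(rS + 1 - S), and the trapezoid area is taken over the scheduled visits. At year 5 with r = 0.90 this is 0.70 × 0.576/(0.576 + 0.36) = 0.431, against a true 0.448. Area over five years:

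| r | Waiting list | Transplant | Difference |
|---|---|---|---|
| 0.95 | 2.797 (-0.9%) | 2.803 (-0.7%) | 0.006 |
| 0.90 | 2.769 (-1.9%) | 2.775 (-1.7%) | 0.007 |
| 0.80 | 2.704 (-4.2%) | 2.712 (-3.9%) | 0.008 |
| 0.70 | 2.627 (-7.0%) | 2.637 (-6.6%) | 0.010 |

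Both groups are biased down, and the schedules add almost nothing. Unequal return rates would matter more. With 95% on the transplant side and 80% on the waiting list, the artefact is 2.803 - 2.704 = 0.10 QALY.

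**Rule B: every due form required from survivors, all deaths kept.** Let k be the forms due, including baseline. The mean is 0.70 × [A + H r^k S]/[(1 - S) + r^k S], with A = (1 - S)/λ - HS, the life-years contributed by those who die.

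Five years: k = 6 (transplant) and 11 (waiting list), A = 0.833. With r = 0.90:
- Transplant: r^k S = 0.340; mean = 0.70 × (0.833 + 1.701)/0.700 = 2.53.
- Waiting list: r^k S = 0.201; mean = 0.70 × (0.833 + 1.004)/0.561 = 2.29.
- False gain 0.24. The dead share is 0.36/0.700 = 51% and 0.36/0.561 = 64%, against a true 36%.

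| Horizon | k, transplant / waiting list | r = 0.95 | r = 0.90 | r = 0.80 |
|---|---|---|---|---|
| 1 year | 4 / 3 | -0.002 | -0.004 | -0.011 |
| 1.5 years | 4 / 4 | 0 | 0 | 0 |
| 3 years | 5 / 7 | 0.02 | 0.05 | 0.12 |
| 5 years | 6 / 11 | 0.12 | 0.24 | 0.35 |

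**Other rules** (same model, index 0.65, five years). Carrying the last value forward gives a difference of 0.002 or less. Linear interpolation to 0 at death gives -0.06 at r = 0.90, a false loss for transplantation.

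**Delisting.** If 20% of five-year survivors had no score, the dead share would be 0.36/(0.36 + 0.64 × 0.80) = 41% instead of 36%.

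**The case against.** The strongest reply is that the plan nowhere says patients with missing forms are dropped. It promises a QALY for each patient, and with post-transplant forms two years apart after year 1, some filling between forms is already implied. With filling by carry-forward, the difference between groups all but disappears. This stands: the bias is a possible result of an open rule, not a necessary result of the text.

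A reader might go further and infer that the denser waiting-list schedule produces a false QALY gain for transplantation. The documents do not support that as a general statement:
- It needs Rule B, which the plan neither states nor excludes. The sign depends on the rule chosen.
- The waiting-list schedule is not denser throughout. In year 1 three post-transplant forms are due against two on the list.
- Aim 4 sets no five-year horizon. Section 2.1 gives a historical mean wait of 9 to 12 months (now markedly longer), so few patients would be due 11 waiting-list forms.
- Larger figures (0.14, 0.31 and 0.74 QALY at five years for 95%, 90% and 80% return) arise only if deaths with a missing earlier form are also discarded. That is not the mechanism at issue.

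Nor can one infer that death is known for everyone from the registry. The plan says so only for post-transplant survival.

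The lack of a stated rule for missing forms, gaps and time after delisting survives all of this.

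**Conclusion.** The concern holds in limited form. Aim 4 combines deaths that need no form with living values that do, and leaves the handling of missing values open. If living non-responders drop out while deaths remain, mean QALYs are biased downward even under completely random non-response. The five-year bias is about -1% to -7% in each group at 95% to 70% return under visit-wise available-case analysis, with at most about 0.01 QALY between groups when return rates are equal. A false gain for transplantation of 0.12 to 0.35 QALY at five years, or 0.02 to 0.12 at three years (95% to 80% return), would need a rule that every due form be present. Up to about 1.5 years even that rule gives none.

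These sizes rest on equal survival of 64% at five years, a constant index of 0.70 and independent returns. Non-response related to health could add to the bias or offset it. The point merits a change because the result depends on a choice that can be fixed now, with data already being collected.

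**What to change.** In Aim 4, replace the per-patient sum over available scores with the following:
- State one horizon common to the transplant and dialysis sides.
- Calculate mean QALYs as the area under S(t) × mean SF-6D among those alive at t. Survival should cover all patients, including those delisted, and the source of deaths for waiting and delisted patients should be named.
- Estimate SF-6D in the living from all returned forms with a mixed model, or multiply impute it for living non-responders only.
- Use the same grid of time points on both sides.
- Obtain the interval for the QALY difference and the ICER by bootstrapping patients.
- Report form return by group and time point.

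The cost is a few sentences and slightly more analysis, with no new questionnaires. Survival status for delisted patients may need to be requested if the registry extract does not already include it. The method assumes SF-6D is missing at random given earlier scores and covariates. That assumption is weakest after delisting, where no forms are due.
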